7.2.2.3. Average Daily Prednisone Dose at the Visit

While on study, the average daily prednisone dose at the visit is the sum of all prednisone doses over 7 consecutive days up to and including the day of interest, divided by 7. Days on which a subject does not have prednisone use recorded will be considered as 0 mg for the day in the calculation of average daily prednisone dose.

The average daily prednisone equivalent dose will be calculated for each scheduled visit. For subjects who withdraw from the study, the early withdrawal visit will only be presented if it slots into a scheduled visit (see Section 13.1.1).

7.2.2.4. Any Decrease from Baseline in Prednisone among Subjects using Prednisone at Baseline (Observed)

The number and percentage of subjects having any decrease compared to baseline among subjects using prednisone at baseline will be presented by visit [T2.05]. These summaries will be based on the average daily prednisone dose at the visit, as calculated in Section 7.2.2.3. No statistical tests will be performed.

A line graph will be produced by visit for the percentage of subjects (±SE) having any decrease in prednisone compared to baseline among subjects using prednisone at baseline [F2.02].

7.2.2.5. Any Increase from Baseline in Prednisone (Observed)

The number and percentage of subjects having any increase compared to baseline will be presented by visit [T2.06]. These summaries will be based on the average daily prednisone dose at the visit, as calculated in Section 7.2.2.3. No statistical tests will be performed.

A line graph will be produced by visit for the percentage of subjects (\pm SE) having any increase in prednisone compared to baseline [F2.03].

8. SAFETY ANALYSES

Safety will be evaluated by the secondary endpoints (adverse events, serious adverse events and adverse events of special interest) and the other safety endpoints of interest (including laboratory summaries and vital signs).

The safety tables and figures will be based on the ITT population and the listings will be based on the enrolled population, unless otherwise specified. See 'RAP mock outputs 200908' document for mock displays.

Safety outputs will report all On Study data (see Section 5.2). Safety data will be summarised using a treatment policy approach, including all data regardless of any Intercurrent Events (ICE).

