1. If participants withdraw from treatment prior to Week 52, in addition to the 8- and 16-week follow-up visit and assessments, an early withdrawal (EW) visit should, if possible, be completed. The EW visit requires identical assessments and procedures to the Week 52 visit. The 8- and 16-week follow-up visits are **NOT** required for participants who are eligible for and are enrolled into the optional access extension phase.
2. 16-week follow-up requires a phone call to collect AEs, concomitant medications and report results of home urine pregnancy test (if applicable) for female participants. NOTE – the 16-week follow-up may be performed at a clinic visit per local requirement.
3. An abbreviated/symptom-driven exam can be done as described in Section 8.8.1
4. Please refer to Section 8.9.1 for the time period for collection of AEs/SAEs.
5. Urine pregnancy test is sufficient for all visits in Part B. A home pregnancy test (urine) will be provided to participants for the 16-week follow-up pregnancy assessment.
6. Cohort 1 (\geq 50 kg at baseline): Study drug to be administered weekly. Wherever the dosing days coincide with clinic visits IP administration in clinic is mandated. PK and/or biomarker sample collection, where specified, must be pre-dose at these visits.
7. Cohort 2 (\geq 30 kg - <50 kg at baseline): Study drug to be administered every 10 days. Wherever the dosing days coincide with clinic visits IP administration in clinic is mandated. PK and/or biomarker sample collection, where specified, must be pre-dose at these visits.
8. Cohort 3 (15 - <30 kg at baseline): Study drug to be administered every 2 weeks. Wherever the dosing days coincide with clinic visits IP administration in clinic is mandated. PK and/or sample collection, where specified, must be pre-dose at these visits.

9. In Part B the dosing frequency may be switched according to any change in body weight. Please refer to Section [6.6](#) Dose Modification. IF a participant switches dosing frequency due to weight changes during Part B, the last IP administration will be according to the schedule provided at Week44. Individual cases will be consulted with and resolved by the Medical Monitor.
10. Samples must be taken pre-dose where the dose is administered on a clinic visit day.

1.3.4. SOA 4 Optional Access Extension Phase - Applies exclusively to eligible participants who complete Part B

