9.3.2. Safety Analyses

All safety analyses will be performed on the ITT Population.

Endpoint	Statistical Analysis Methods
Secondary	
Endpoints:
 
Incidence of adverse events, serious adverse events, and adverse events of special interest (AESI) through Week 52.
 
Analysis:
 
Descriptive statistics will be used to summarize AEs, SAEs, and AESIs. The frequency of AEs will be tabulated by MedDRA system organ class (SOC) and preferred term.

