2.2. Study Objectives and Endpoints

[figure not shown]
The protocol defined objectives and endpoints (Protocol Section 3) are shown in Table 2.

 Table 2
 Protocol defined objectives and endpoints

Objectives	Endpoints		
Primary Objectives	Primary Endpoints		
To characterize the pharmacokinetic (PK) profile of belimumab 200 mg SC in pediatric systemic lupus erythematous (SLE) participants	 Observed belimumab concentrations at Week 12 Steady-state PK parameters: Cavg (AUC), Cmax, Cmin (based on population PK estimates)¹ 		
Secondary Objectives: Safety	Secondary Endpoints: Safety		
To evaluate the safety and tolerability of belimumab 200 mg SC in pediatric SLE participants	Incidence of adverse events, serious adverse events and adverse events of special interest through Week 52		
Secondary Objectives: Biomarkers	Secondary Endpoints: Biomarkers		
To characterize the pharmacodynamic (PD) profile of belimumab 200 mg SC in pediatric SLE participants	 Change from baseline in biomarkers (C3/C4, anti-dsDNA, B cell subsets, and immunoglobulins) at Weeks 12 and 52 		
Exploratory Objectives: Efficacy	Exploratory Endpoints: Efficacy		
To characterize the impact of belimumab 200 mg SC on disease activity in pediatric SLE participants	 Percentage of subjects with a ≥ 4 point reduction from baseline in SELENA SLEDAI at Weeks 12 and 52 		

¹ Note that these endpoints will be described in a separate RAP written by Clinical Pharmacology Modelling & Simulation (CPMS) and analyses will be presented separately.

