3.2. Final Analyses

There will be two Database Locks (DBL) for this study.

The first DBL corresponds to all data collected in Part A and Part B of the study (including Follow Up assessments). The results will be reported in the primary CSR.

The second DBL corresponds to the access extension phase of the study. This data will predominantly be collected on paper Case Report Forms (CRFs) and is therefore not discussed within this document. The results will be reported in a synoptic CSR at the end of the access extension phase. No formal statistical analyses will be performed in the optional access extension phase.

Data for the access extension phase that is collected within the eCRF is limited to the following:

Data	Reported
Subject continuation in the access extension phase (Yes/No)	Primary CSR & Synoptic CSR
Pregnancy status during the access extension phase	Synoptic CSR
Phase conclusion for the access extension phase (Date of completion/withdrawal and reason for withdrawal if applicable)	Synoptic CSR

For subjects who do not enter the access extension phase, all data will be retained in the Primary datasets and reported in the Primary CSR.

For subjects who do enter the access extension phase, all data will be retained in the Primary datasets and reported in the Primary CSR up to and including the End of Study conclusion date recorded on the eCRF. This date represents the end of each subjects Part A and B data (including Follow Up assessments if applicable). All data collected after that date will be reported in the Synoptic CSR. Any data collected after this date in the eCRF for disposition or on log forms (AEs or concomitant medications) will be removed from the Primary datasets to avoid double reporting.

The first DBL will be performed after completion of the following sequential steps:

- 1. The last subject's completion of Part B (including all 16 week follow-up visits)
- 2. All required database cleaning activities have been completed
- 3. All criteria for reporting the study have been met, including:
 - Review of Protocol Deviations
 - Categorization of Adverse Events of Special Interest (AESI)
 - Review of dropouts
- 4. DBL declared by Data Management

The second DBL will be performed after completion of the following sequential steps:

- 1. The last subject's completion of the last visit in the optional access extension phase
- 2. All required database cleaning activities have been completed
- 3. DBL declared by Data Management

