5.2. On Study Definition

On study is defined as Day 1 until the date of study completion or study withdrawal (including LTFU and death), excluding the access extension phase (see Section 3.2).

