8.1. Secondary Endpoint - Adverse Events

8.1.1. Adverse Events Analyses

Adverse events analyses including the analysis of adverse events (AEs), Serious adverse events (SAEs) and AEs of special interest (AESIs) will be based on GSK Core Data Standards. All subjects will be followed for safety up to 16 weeks post-treatment.

All AEs will be classified using the current standard GSK Medical Dictionary for Regulatory Activities (i.e. MedDRA version in use at the time of reporting), and grouped by System Organ Class (SOC) and/or Preferred Term (PT). The MedDRA version is detailed on every table that uses MedDRA. The investigator will evaluate all AEs with respect to seriousness, severity and causality. The severity of an AE is to be determined using the Assessment of Intensity provided in Appendix 2 of the protocol, if a grade is provided for the AE of interest.

For the following summaries, only treatment-emergent AEs will be summarized, unless otherwise stated. Treatment-emergent AEs are defined in Section 13.2.2 based on start date/time of AE versus first dose date/time of study treatment. AEs with missing start and/or stop dates will be assumed to be treatment-emergent.

The duration of the AE will be calculated as follows:

Duration of AE (days) = Date of AE resolution – AE start date + 1.

If the AE is ongoing the duration will be left blank and no imputation will be done.

Common non-serious AEs will be defined as two or more subjects experiencing the event.

An overall summary of AEs will be presented showing the number and percentage of subjects with at least one: AE, related AE, SAE, severe AE, SAE and/or severe AE, AE resulting in study agent discontinuation and death [T3.01].

The number and percentage of subjects experiencing an AE will be summarized for each of the following AE categories:

- All AEs (by SOC and PT; by PT only) [T3.02, T3.03]
- All SAEs (by SOC and PT) [T3.04]
- AEs resulting in study agent discontinuation (by PT only) [T3.05]
- Common non-serious AEs (number of subjects and occurrences) (by SOC and PT) [T3.06]
- SAEs (number of subjects and occurrences) (by SOC and PT) [T3.07]
- Study drug related Non-Serious AEs (by PT only) [T3.08]
- Study drug related fatal and non-fatal SAEs (by PT only) [T3.09]
- AEs by severity (by SOC and PT) [T3.10]
- Study drug related AEs by severity (by SOC and PT) [T3.11]

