13.2.2. Treatment Emergent Flag for Adverse Events

Flag	Definition
Treatment	If AE onset date is on or after treatment start date, having been absent pre-
Emergent	treatment, or the AE worsens relative to the pre-treatment state.

NOTES:

- Time of study treatment dosing and start/stop time of AEs should be considered, if collected.
- Worsening of an event is captured in the eCRF by modifying the severity of the original event; therefore, worsening is accounted for in how the AE is recorded and no programming is required to identify worsening events.

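### The secondary safety endpoint stops at Week 52, but the SAP's adverse event tables run to the end of follow-up, up to about Week 68

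*SAP*

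**What the plan says.** Protocol Section 9.3.2 gives the endpoint as "Incidence of adverse events, serious adverse events, and adverse events of special interest (AESI) through Week 52", and SAP Section 2.2 repeats it. SAP Section 2.1 declares no change from the protocol's planned analysis.

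The analysis rules set a different window:

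- SAP Section 8: "Safety outputs will report all On Study data (see Section 5.2".
- SAP Section 5.2: "On study is defined as Day 1 until the date of study completion or study withdrawal". Only the access extension is excluded, with a reference to Section 3.2.
- SAP Section 3.2 places follow-up assessments inside the Part A and B data, the first database lock and the primary CSR.
- SAP Section 8.1.1, which describes the endpoint tables: "All subjects will be followed for safety up to 16 weeks post-treatment".
- SAP Section 13.2.2 starts its treatment-emergent definition with "If AE onset date is on or after treatment start date, having been absent" and gives no last day.

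Extension entrants are handled differently. Under Protocol Section 1.3.3, footnote 1, the 8- and 16-week Part B follow-up visits are not "required for participants who are eligible for and are enrolled into the optional access extension phase". SAP Section 3.2 adds that, for these participants, data dated after the end-of-study date and held "on log forms (AEs or concomitant medications) will be removed from the Primary datasets to avoid double reporting".

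**The concern.** The AE, SAE and AESI tables that are meant to report the endpoint carry no Week 52 limit in the SAP text. The one mention of Week 52 in the AESI section (8.1.5) stops an unresolved event from being reported twice; it does not limit onset.

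Two things follow. First, the reported percentage is not the endpoint named in the protocol. Second, it depends partly on how many Part B completers enter the extension. Protocol Section 6.7.1.2 makes that a matter of age, IV licensing, suitability of the IV form, logistics and investigator-judged clinical benefit, so the observation window is partly set by factors unrelated to the safety question.

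The study is meant to support extrapolation of safety from the pediatric IV and adult SC trials (Protocol Section 2). The pediatric IV reference rates come from a 52-week phase, so a figure reaching Week 68 is not like for like with them.

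**Working it through.** **Timing, from the plan's own figures.** SAP Appendix 1 puts the Week 52 visit at Day 365 and the 16-week follow-up at Day 477.

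- 365 + 16 × 7 = 477, and (477 − 1)/7 = 68.0 weeks. This reproduces Day 477 and the protocol schedule's Week 68.
- 5 + 52 + 16 = 73 weeks reproduces the protocol's maximum duration for Parts A and B.
- Counted from the last scheduled dose, 16 weeks later is Week 67.0 (Cohort 1, last dose Week 51), Week 67.4 (Cohort 2, Day 361) or Week 66.0 (Cohort 3, Week 50). About Week 68 is a fair description.
- Excess over the endpoint window: (477 − 365)/7 = 16 weeks, and 16/52 = 30.8%.

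**Who contributes after Week 52.** Part B completers outside the extension add up to 16 weeks. Participants who withdraw with a last dose after about Week 36 (52 − 16) can add less. Those who stop earlier, including participants who leave after Part A, finish follow-up before Week 52. Extension entrants stop at about Week 52 in the primary datasets.

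**Illustrative size.** The documents do not give the number of added events. The illustration takes 52-week proportions from the belimumab arm of the pediatric IV study (Protocol Section 2.2.1.4): SAEs 17.0%, infection AEs 56.6%. It assumes a constant hazard for the first event and 28 participants, of whom a fraction *f* is followed to Week 68 while the rest are unaffected by the cut.

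- P68 = 1 − (1 − P52)^(68/52)
- Reported proportion = P52 + *f* × (P68 − P52)
- SAEs: 1 − 0.83^(68/52) = 0.216, a difference of 0.046
- Infection AEs: 1 − 0.434^(68/52) = 0.664, a difference of 0.098

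| Event | Week 52 | *f* = 0.25 | *f* = 0.5 | *f* = 1 (maximum) |
|---|---|---|---|---|
| SAE | 17.0% | 18.2% | 19.3% | 21.6% |
| Extra points (participants of 28) | | 1.2 (0.3) | 2.3 (0.6) | 4.6 (1.3) |
| Infection AE | 56.6% | 59.1% | 61.5% | 66.4% |
| Extra points (participants of 28) | | 2.5 (0.7) | 4.9 (1.4) | 9.8 (2.8) |

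**Against sampling error.** The exact 95% confidence interval for 5 of 28 is 6% to 37%.

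**The case against.** The strongest defence is that on-study time might already end at Week 52. Protocol Section 4.4 and SAP Section 13.4.1 define completion of the primary study by the Week 52 visit, so the completion date in SAP Section 5.2 could be read that way. The rest of the SAP does not support this. Section 5.2 points to Section 3.2, where the end-of-study date includes follow-up where applicable. Section 8.1.1 follows safety for 16 weeks, Section 8.2.2 counts follow-up assessments in the worst laboratory grade, and Section 9.1 uses on-study PK data and then needs a special rule for the Week 8 follow-up. A programmer following the SAP would include follow-up events.

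Other points stand in part:

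- The mock displays and the program safety analysis plan are separate documents. A limit in a table title there cannot be excluded; the SAP text has none.
- The exposure table (T1.20) is labelled as running to Week 52, but scheduled dosing ends by then anyway. That contrast proves little about the AE tables.
- Extension entrants do have follow-up of their own after the extension. It collects SAEs and is reported in the synoptic CSR, so it does not lengthen their window in the primary tables.
- All AEs are listed by subject, so a careful reader could identify the later events.
- The effect is small, there is no comparator or hypothesis test, and collecting events during follow-up is sound safety practice.

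These points limit the consequence. They do not supply the missing endpoint analysis.

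**Conclusion.** The concern holds. The SAP as written never tabulates the protocol's secondary safety endpoint. Its incidence figures combine a window of about 52 weeks for extension entrants with about 68 weeks for other Part B completers.

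The likely distortion is a fraction of a participant for SAEs and about one for infections if half the participants are followed to Week 68. The upper bounds are 1.3 and 2.8 participants. These sizes rest on the constant-hazard assumption, including through off-treatment follow-up, and on rates borrowed from the IV study. The effect would be smaller for reactions that cluster at the first doses. The issue should be corrected because endpoint and analysis disagree and the correction is cheap; it does not threaten the study's conclusions.

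**What to change.** For the secondary endpoint, restrict the incidence tables (T3.01 to T3.04 and T3.06 to T3.12) to treatment-emergent events with onset up to the Week 52 visit, or Day 365 for participants without that visit. An early withdrawal visit slotted to Week 52 under Appendix 1 should not count as that visit. Within the window, count every event whether on or off treatment, which keeps the treatment-policy approach. The Day 365 rule also covers late withdrawers.

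Keep the all-on-study tables as supplementary and show events after Week 52 separately, so no safety information is lost. Label T3.43 and T3.44 with the window they use, so that they do not appear to conflict with the endpoint tables. State in SAP Section 5.2 the exact date on which on-study time ends.

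The cut does not correct for participants observed for less than 52 weeks because they declined Part B or withdrew early. Events per 100 participant-years in the same window could be added as a supportive summary.

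If the sponsor does intend the longer window, the alternative is to amend the endpoint wording and declare the change in SAP Section 2.1.

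The cost is SAP wording and one onset-date filter in programming. All the dates are already collected, and no added data or participants are needed.

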8.1. Secondary Endpoint - Adverse Events

8.1.1. Adverse Events Analyses

Adverse events analyses including the analysis of adverse events (AEs), Serious adverse events (SAEs) and AEs of special interest (AESIs) will be based on GSK Core Data Standards. All subjects will be followed for safety up to 16 weeks post-treatment.

All AEs will be classified using the current standard GSK Medical Dictionary for Regulatory Activities (i.e. MedDRA version in use at the time of reporting), and grouped by System Organ Class (SOC) and/or Preferred Term (PT). The MedDRA version is detailed on every table that uses MedDRA. The investigator will evaluate all AEs with respect to seriousness, severity and causality. The severity of an AE is to be determined using the Assessment of Intensity provided in Appendix 2 of the protocol, if a grade is provided for the AE of interest.

For the following summaries, only treatment-emergent AEs will be summarized, unless otherwise stated. Treatment-emergent AEs are defined in Section 13.2.2 based on start date/time of AE versus first dose date/time of study treatment. AEs with missing start and/or stop dates will be assumed to be treatment-emergent.

The duration of the AE will be calculated as follows:

Duration of AE (days) = Date of AE resolution – AE start date + 1.

If the AE is ongoing the duration will be left blank and no imputation will be done.

Common non-serious AEs will be defined as two or more subjects experiencing the event.

An overall summary of AEs will be presented showing the number and percentage of subjects with at least one: AE, related AE, SAE, severe AE, SAE and/or severe AE, AE resulting in study agent discontinuation and death [T3.01].

The number and percentage of subjects experiencing an AE will be summarized for each of the following AE categories:

- All AEs (by SOC and PT; by PT only) [T3.02, T3.03]
- All SAEs (by SOC and PT) [T3.04]
- AEs resulting in study agent discontinuation (by PT only) [T3.05]
- Common non-serious AEs (number of subjects and occurrences) (by SOC and PT) [T3.06]
- SAEs (number of subjects and occurrences) (by SOC and PT) [T3.07]
- Study drug related Non-Serious AEs (by PT only) [T3.08]
- Study drug related fatal and non-fatal SAEs (by PT only) [T3.09]
- AEs by severity (by SOC and PT) [T3.10]
- Study drug related AEs by severity (by SOC and PT) [T3.11]

The tabular summary for each category of AE listed above will include the number of subjects with any event (incidence), the number of subjects with any event in each SOC (where applicable), plus the number of subjects with any event in each PT.

For the tables by severity, the number and percentage of subjects will be summarized as mild, moderate or severe based on the maximum severity observed across all PTs, within the SOC for a given subject. Additionally, the number and percentage of subjects will be summarized as mild, moderate, or severe based on the maximum severity observed within each PT and within each SOC.

By default, AEs will be sorted by MedDRA SOCs, in descending order from the SOC with the highest total incidence to the SOC with the lowest total incidence – firstly based on the number of subjects and then based on the number of occurrences. If the total incidence for any two or more SOCs is equal (based on number of subjects and occurrences), the SOCs will be presented in alphabetical order. Only SOCs with observed AE PTs will be presented. The sort order for MedDRA PTs within each SOC will be repeated, i.e. PTs will be presented in descending order of incidence (number of subjects, then number of occurrences) and then alphabetically if the incidence is equal.

The table displaying all AEs by SOC and PT may be repeated for subgroups for post-hoc analyses.

A listing of all AEs will be presented by subject [L3.01].

A listing that displays which subjects reported each AE will also be produced. AEs will be sorted by SOC and PT [L3.02].

A listing of all AEs resulting in study agent discontinuation will be presented by subject [L3.05].

The hierarchical relationship between MedDRA SOCs, PTs and verbatim text will be displayed in a listing for all AEs [L3.09].

8.1.2. Additional Adverse Event Summaries to Assess the Impact of the Coronavirus Disease 2019 (COVID-19) Pandemic

A listing will be produced to show COVID-19 assessments and symptoms for all subjects with a suspected, probable or confirmed COVID-19 infection throughout the study [L3.08]. This listing will be based on information collected on the COVID-19 Coronavirus Infection Assessment CRF page.

No additional summaries/listings will be produced due to the timing of recruitment in relation to the COVID-19 pandemic. The first subject was screened for the study in November 2019 and COVID-19 pandemic environment onset dates for each Country are presented in Section 13.4.6. Therefore, nearly all on-treatment data was collected during the COVID-19 pandemic and summaries split by pre COVID-19 or during COVID-19 would not be informative.

